3.8. Analysis Windows

3.8.1. Definition of Study Day

Study Day 1 for the Randomized Phase analysis is defined as the day when the first dose of study drug (ie, B/F/TAF, DTG +F/TDF) was taken, as recorded on the Study Drug Administration eCRF.

Last Dose Date for the Randomized Phase analysis is the latest of the blinded study drug end dates recorded on the Study Drug Administration eCRF form with "Permanently Withdrawn" box checked for participants who prematurely discontinued or completed study drug in the "Blinded Treatment" study phase according to the Study Drug Completion eCRF.

If last dose date for the Randomized Phase analysis is missing (eg, only year of last dose date is known or completely missing due to lost to follow-up), the latest of the randomized study drug start dates and end dates, or the latest clinical visit dates and the laboratory visit dates prior to the first dose date of B/F/TAF in the extension phase (if applicable), excluding the date of 30-day follow-up visit, will be used to impute the last dose date. For other partial missing last dose date, please see the programming specifications for imputation rule details.

Study Day 1 for the all B/F/TAF analysis is defined as:

- For participants who actually received B/F/TAF in the randomized phase of this study (ie, B/F/TAF group), Study Day 1 for the all B/F/TAF analysis is defined as the day when the first dose of B/F/TAF in the randomized phase was taken, as recorded on the Study Drug Administration eCRF form.
- For participants who actually received DTG + F/TDF in the randomized phase of this study and then receive at least 1 dose of B/F/TAF in the extension phase (ie, DTG + F/TDF to B/F/TAF group), Study Day 1 for the all B/F/TAF analysis is defined as the day when the first dose of B/F/TAF in the extension phase was taken, as recorded on the Study Drug Administration eCRF form.

Last Dose Date for the All B/F/TAF Analysis is the latest of B/F/TAF (including both phases) end dates recorded on the Study Drug Administration eCRF form with "Permanently Withdrawn" box checked for participants who prematurely discontinued or completed study drug in either or both of the study phases ("Blinded Treatment", "Open-Label Treatment") according to the Study Drug Completion eCRF.

If the last dose date for the all B/F/TAF analysis is missing (eg, only year of last dose date is known or completely missing due to lost to follow-up), the latest of the B/F/TAF (including both phases) start dates and end dates, the latest clinical and laboratory visit dates, excluding the 30-day follow-up visit date, will be used to impute the last dose date.

Study Days are calculated relative to Study Day 1 for either the randomized phase analysis or the all B/F/TAF analysis, as appropriate. For events that occurred on or after the Study Day 1 date of either analysis, study days are calculated as (visit date minus the date of Study Day 1 plus 1). For events that occurred prior to Study Day 1 for either analysis, study days are calculated as visit date minus the date of Study Day 1.

Last Study Date is the latest of the study drug (including B/F/TAF and DTG + F/TDF in both phases) start dates and end dates, the clinic visit dates, and the laboratory visit dates, including the 30-day follow-up visit date.

Baseline Value is defined as the last nonmissing value obtained on or prior to Study Day 1 for either the randomized phase analysis or the all B/F/TAF analysis, as appropriate. Participants who actually received DTG + F/TDF in the randomized phase and received at least 1 dose of B/F/TAF in extension phase will have a new baseline value for the All B/F/TAF analysis.

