6.5. Treatment Assessments (Week 4 – 96)

The following evaluations are to be completed at the end of Weeks 4, 8, 12, 24, 36, 48, 60, 72, 84 and 96 unless otherwise specified.

Study visits are to be completed within ± 2 days of the protocol-specified visit date (based on the Day 1 visit) through Week 12 and completed within ± 6 days of the protocol-specified visit date through Week 96, unless otherwise specified. The visit window at Weeks 48 and 96 will be ± 6 weeks of the protocol-specified visit date, and this clinical visit window coincides with the Weeks 48 and 96 statistical analysis window for HIV-1 RNA.

Regularly scheduled evaluations will be made on all subjects whether or not they continue to receive study drug.

- Review of AEs and changes in concomitant medications
- Complete physical examination (**Weeks 24, 48, 96**) (urogenital/anorectal exams will be performed at the discretion of the Investigator) or symptom-directed physical examination as needed
- Vital signs measurement (blood pressure, pulse, respiration rate, and temperature), including weight
- Obtain blood and urine samples as described in Section 6.10
- Provide subject dosing diary to all subjects (**Weeks 4, 8, 12 and 24**)
- Dosing diaries will be collected from subjects for the trough and post-dose PK blood sample collection as noted in Section 6.10. If a dosing diary is not returned the site may ask the subject for the time of the last dose and if it was taken with or without food.
- Document study drug dispensation and accountability for all study drugs dispensed.

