6.6.2. End of Blinded Treatment Visit Assessments

Once the last subject completes their Week 96 visit and Gilead completes the Week 96 analysis, all subjects will return to the clinic (preferably within 30 days) for an End of Blinded Treatment Visit. At the End of Blinded Treatment Visit, if safety and efficacy of B/F/TAF FDC is demonstrated for the HIV-1 and HBV coinfecting subjects following review of unblinded data, subjects in a country where B/F/TAF FDC is not available will be given the option to receive B/F/TAF FDC in an open label extension phase for up to 48 weeks, or until the product becomes accessible to subjects through an access program, or until Gilead Sciences elects to discontinue the study in that country, whichever occurs first.

Subjects who receive the open-label B/F/TAF FDC will return for study visits every 12 weeks.

Subjects who complete the study through the End of Blinded Treatment Visit and do not continue on the open label B/F/TAF FDC extension will be required to return to the clinic for a 30-Day Follow-up visit. Subjects who have discontinued drug study prior to the End of Blinded Treatment Visit will not be eligible for the open-label rollover extension; these subjects will be asked to continue attending the scheduled study visits through the End of Blinded Treatment Visit and discontinue the study after the End of Blinded Treatment Visit.

Treatment assignments will be provided to the investigators within 30 days of the last subject completing the End of Blinded Treatment Visit.

The following will be performed at the End of Blinded Treatment Visit:

- Review of AEs and changes in concomitant medications
- Complete physical examination (urogenital/anorectal exams will be performed at the discretion of the Investigator)
- Vital signs measurement (blood pressure, pulse, respiration rate, and temperature), including weight
- Obtain blood and urine samples as described in Section 6.10
- Document study drug dispensation, if applicable, and accountability for all study drugs dispensed
- Subjects who wish to continue in the Open-Label Rollover extension study will receive open label B/F/TAF.

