6.11. Assessments for Premature Discontinuation from Study

If a subject discontinues study drug in the blinded phase of the study (for example, as a result of an AE), every attempt should be made to keep the subject in the study, and continue to perform the required study procedures until the End of Blinded Treatment Visit. If this is not possible or acceptable to the subject or investigator, the subject may be withdrawn from the study.

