For subjects with a partial last dosing date (ie, month and year of last dose are known), the minimum of { (the latest of the dispensing dates of study drug bottles, study drug start dates and end dates (based on EX dataset with study drug in extension phase), and the imputed last dose date [day imputed as 15])} will be used as the final imputed last dose date. However, if dispensing date's month is after last dose date's month, data query is needed. If subject died and the death date is complete (ie, not partial date) and before the imputed last study date, the complete death date should be used as the imputed last study date.

b) Last Study Date is the latest of the randomized or extension phase (if available) study drug start dates and end dates, the clinic visit dates, and the laboratory visit dates, including the 30-day follow-up visit date. If study drug start dates or end date is partially missing (ie, only year and month are known), the day will be imputed as 15 for the purpose of this analysis.

If participant died and the death date is complete (ie, not partial date) and before the imputed last study date, the complete death date should be used as the imputed last study date.

12. Toxicity Grades:

Two type of treatment emergent lab abnormalities flag variables will be derived for laboratory data as applicable. For treatment emergent flag used in listing for randomized analysis set, the baseline toxicity grade will be based on baseline value defined as the last nonmissing value obtained on or prior to the first dose of randomized study drug. For treatment emergent flag used for the All B/F/TAF analysis summary and listing using all B/F/TAF analysis set, the baseline toxicity grade will be based on baseline value defined as the last nonmissing value obtained on or prior to the first dose of B/F/TAF.

Treatment-emergent laboratory abnormalities will be summarized for all B/F/TAF analysis, following the same rule bellows.

- a) For toxicity grade summaries, include all postbaseline graded results up to 30 days after the last dose of study drug B/F/TAF, not just those used in by-visit summaries.

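### The imputation rule for a missing or year-only last-dose date can count off-drug time as B/F/TAF exposure and on-treatment data for participants who stopped blinded drug but stayed on visits

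*SAP*

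**What the plan says.** SAP 3.8.1 (Definition of Study Day) covers last-dose dates that are missing, with the example "only year of last dose date is known or completely missing due to lost to follow-up". For the All B/F/TAF analysis it takes the latest of the B/F/TAF start and end dates in both phases and the visit dates: "the latest clinical and laboratory visit dates, excluding the 30-day follow-up visit date, will be used to impute the last dose date". The randomized-phase rule is parallel. It adds only that visits must precede the first extension dose, where there is one: "laboratory visit dates prior to the first dose date of B/F/TAF in the extension phase (if applicable), excluding the date of 30-day follow-up visit". Neither rule excludes visits made after drug was stopped, and neither uses a recorded year as an upper limit.

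The protocol retains participants who stop blinded drug. Section 6.5: "Regularly scheduled evaluations will be made on all subjects whether or not they continue to receive study drug". Section 6.11: "every attempt should be made to keep the subject in the study, and continue to perform the required study procedures". Section 6.6.2 sets how long this lasts: "these subjects will be asked to continue attending the scheduled study visits through the End of Blinded Treatment Visit".

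When month and year are known, SAP Appendix 7 item 11 applies a different rule. It uses dispensing dates, dosing dates and day 15 of the month, not visit dates. In its extension-phase paragraph the death limit reads: "the complete death date should be used as the imputed last study date". The randomized-phase paragraph applies the same limit to the last dose date.

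**The concern.** The latest-visit rule suits someone lost to follow-up while on drug, since the last contact is then a fair stand-in for the last dose. It does not suit someone who stopped drug and kept attending, whose latest visit may be months or years after the last dose.

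The one safeguard misses this group. Leaving out the 30-day visit suggests that the SAP means to keep post-drug contacts out. But Protocol 6.8.2 does not require a 30-day visit from stoppers who attend at least one later visit, so the exclusion works for those who leave and does nothing for those who are retained. The rule is also looser where information is poorer: a date known to the month is held to dispensing and dosing records, while a date known to the year is not held even to that year.

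Several outputs depend on the last-dose date:
- duration of exposure (SAP 4.2.1);
- the +1-day on-treatment cut for CD4, HBV DNA and the other HBV endpoints (6.3.2.2 to 6.3.2.4) and for treatment-emergent ALT elevation (7.2.5);
- the +30-day window for adverse events, deaths and laboratory abnormalities (7.1.5, 7.1.6, 7.2.2).

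ALT matters most. Protocol 7.5.4 separates an on-treatment flare from an exacerbation after stopping, and a late imputed date would count the second as the first. Virologic Rebound Schema note e lets a participant move to a new regimen and stay in the study, so a response to other drugs could also be counted as on-treatment.

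**Working it through.** The plan states no figure for this rule, so the check is a reading of the text plus date arithmetic.

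**Inputs.** Visits fall at Weeks 4, 8 and 12 and every 12 weeks thereafter (Protocol synopsis and 6.5). The imputed date is the latest visit (SAP 3.8.1). Exposure is last dose minus first dose plus 1 (SAP 4.2.1). The on-treatment cut is last dose plus 1 day (SAP 6.3.2.2). Some SAP sections write permanent discontinuation instead of last dose date; I read the two as the same date, in line with SAP Section 7, which equates the study drug stop date with the last dose date. The stop weeks, and attendance after stopping, are assumptions.

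**Formulas.** Excess exposure in weeks = (day of last visit − day of true stop) / 7. Misclassified visits = scheduled visits later than true stop + 1 day and no later than the imputed date + 1 day.

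**Main example.** Stop at Week 12 (Day 84), last visit at Week 96 (Day 672): (672 − 84) / 7 = 84 weeks. The visits at Weeks 24, 36, 48, 60, 72, 84 and 96 are misclassified, seven in all. One such person raises mean exposure in a planned arm of 120 by 84 / 120 = 0.7 weeks.

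| True stop | Last visit | Excess (weeks) | Off-drug visits counted as on-treatment |
|---|---|---|---|
| Week 8 | Week 96 | 88 | 8 |
| Week 12 | Week 96 | 84 | 7 |
| Week 24 | Week 96 | 72 | 6 |
| Week 48 | Week 96 | 48 | 4 |
| Week 84 | Week 96 | 12 | 1 |
| Week 8 | Week 144 (assumed) | 136 | 12 |

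The last row matters because the End of Blinded Treatment Visit follows the last participant's Week 96 visit and the Week 96 analysis, so early enrollees may be followed well past Week 96.

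**Known year.** In the main example the gap is 672 − 84 = 588 days. No calendar year exceeds 366 days, so the imputed date must fall in a later year than the one recorded.

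**With the discontinuation visit as the limit.** Protocol 6.8.1 asks for that visit within 72 hours of stopping, so if it was held on time the excess is at most 3 / 7 = 0.4 weeks.

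**Who is affected in the tables.** SAP Section 3 bases all final-analysis tables on the All B/F/TAF analysis; randomized-phase dates support listings only. Protocol 6.8.2 ends scheduled visits for anyone who stops in the open-label phase. The problem in the tables is therefore confined to B/F/TAF-arm participants who stopped in the blinded phase.

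**Death limit in Appendix 7 item 11.** This sits in the rule for a known month and year. Dispensing and dosing dates cannot follow death, so only the day-15 imputation can overshoot. The worst case is a death on day 1 of the recorded month: 15 − 1 = 14 days.

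**The case against.** The strongest reply is that the rule will rarely be triggered in the harmful setting. The SAP's own example of a completely missing date is loss to follow-up. The 84-week case needs a participant who attends for 84 weeks while the site cannot name even the month in which drug stopped. That would be despite a discontinuation visit within 72 hours, drug accountability at treatment visits, and an eCRF field for the permanent stop date. This stands: the number affected is probably small, and the documents give no count.

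The consequences are also bounded. The All B/F/TAF analysis makes no treatment comparison. Protocol 7.3 collects non-serious adverse events only to 30 days after the last dose, so a falsely long window adds few of them, although serious events and laboratory data continue. The HIV-1 RNA analysis in SAP 6.3.2.1 states no on-treatment cut. The effects do not all favor one side: off-drug rebound or flare counts against B/F/TAF, while suppression on another regimen counts for it.

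A reader might infer that the rule always overstates exposure. It does not. For someone lost to follow-up, the last visit is often a dispensing visit, and tablets taken afterwards are not counted, so exposure can be understated. The upward error is specific to retained stoppers.

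None of this makes the latest visit a sound stand-in for the last dose in a participant recorded as having stopped drug earlier.

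**Conclusion.** The rule as written is wrong for one identifiable group: B/F/TAF-arm participants who stopped blinded drug, stayed on visits, and have a last-dose date that is missing or known only to the year. For each, the excess is 12 to 88 weeks if the last visit is Week 96, depending on the assumed stop week, and more if blinded visits ran longer. The effect on group summaries is small unless several participants are involved.

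A reader might also infer that the Week 48 or Week 96 comparisons are affected. The documents do not support that: SAP Section 6 says those analyses were done earlier, under SAPs not among these documents, and the final-analysis tables at issue are descriptive. Nor is the DTG + F/TDF to B/F/TAF group materially exposed, because open-label stoppers attend no further scheduled visits. The death-limit wording is a genuine slip, but a separate one worth about two weeks at most; it should not be read together with the 84-week figure.

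**What to change.** Amend SAP 3.8.1, for both analyses, when the last-dose date is missing or known only to the year:

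1. If premature study drug discontinuation is recorded and the participant stayed in the study, use only visits up to and including the Early Study Drugs Discontinuation Visit. If that visit did not occur, use the latest dispensing or dosing date, as Appendix 7 item 11 already does for partial dates.
2. Keep the latest-visit rule for participants lost to follow-up while on drug.
3. Where the year is known, cap the imputed date at 31 December of that year.

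Do not cap at the last drug return date. SAP 4.2.2 expects some bottles not to be returned, and such a cap would cut genuine exposure. For example, a participant on drug at Week 48 who last returned bottles at Week 36 would lose 48 − 36 = 12 real weeks.

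Separately, in the Extension Phase Last Dose Date paragraph of Appendix 7 item 11, replace last study date with last dose date, so that the death limit applies to the last dose as it does in the randomized-phase paragraph.

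The cost is SAP wording and a few lines of code, using data already collected. SAP Section 1 provides for changes after finalization to be documented in the clinical study report; that report can also give the number of participants affected, including if it is zero.

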3.8.2. Analysis Windows

Participant visits might not occur on protocol-specified days. Therefore, for the purpose of analysis, observations will be assigned to two different sets of analysis windows based on the following tables: the analysis windows for the randomized phase analysis are derived relative the Study Day 1 for the randomized phase analysis, while the analysis windows for the all B/F/TAF analysis are derived relative the Study Day 1 for the all B/F/TAF analysis.

The analysis windows for HIV-1 RNA, HBV DNA, CD4+ cell count, CD4 %, hematology, chemistry, urinalysis, urine pregnancy laboratory tests, eGFR_{CG}, vital signs, weight and BMI are presented in Table 3-1 and Table 3-3 for the randomized phase analysis and the All B/F/TAF analysis separately.

Table 3-1.

Analysis Windows for HIV-1 RNA, HBV DNA, CD4+ cell count, CD4%, Hematology, Chemistry, Urinalysis, and Serum/Urine Pregnancy Laboratory Tests, eGFR_{CG}, Vital Signs, Weight and BMI for the Randomized Phase Analysis

Visit ID	Nominal Day	Lower Limit	Upper Limit
Baseline			1
Week 4	28	2	42
Week 8	56	43	70
Week 12	84	71	126
Week 24	168	127	210
Week 36	252	211	294
Week 48	336	295	378
Week 60	420	379	462
Week 72	504	463	546
Week 84	588	547	630
Week 96	672	631	714
Week K (K is every 12 weeks after previous visit)	K*7	(K-6)*7+1	(K+6)*7

Table 3-2 Analysis Windows for HIV-1 RNA, HBV DNA, CD4+ cell count, CD4%, Hematology, Chemistry, Urinalysis, and Serum/Urine Pregnancy Laboratory Tests, eGFR_{CG}, Vital Signs, Weight and BMI for the All B/F/TAF Analysis

	B/F/TAF Group			DTG + F/TDF to B/F/TAF		
Visit ID	Nominal Day	Lower Limit	Upper Limit	Nominal Day	Lower Limit	Upper Limit
Baseline			1			1
Week 4	28	2	42	NA	NA	NA
Week 8	56	43	70	NA	NA	NA
Week 12	84	71	126	84	2	126
Week 24	168	127	210	168	127	210
Week 36	252	211	294	252	211	294
Week 48	336	295	378	336	295	378
Week 60	420	379	462	420	379	462
Week 72	504	463	546	504	463	546
Week 84	588	547	630	588	547	630
Week 96	672	631	714	672	631	714
Week K	K*7	(K-6)*7+1	(K+6)*7	K*7	(K-6)*7+1	(K+6)*7

NA = Not applicable

Note: For the B/F/TAF group, Study Day 1 is the first dose date of the B/F/TAF received in the randomized phase.

Note: For the DTG + F/TDF to B/F/TAF group, Study Day 1 is the first dose date of the B/F/TAF received in the extension

Note: Week K is every 12 weeks after the previous visit.

The analysis windows for HBV serology (including HBsAb, HBsAg, hepatitis B e-antigen [HBeAg], and hepatitis B e-antibody [HBeAb]) are presented in Table 3-3 and Table 3-4.

Table 3-3. Analysis Windows for HBV Serology for the Randomized Phase Analysis

Visit ID	Nominal Day	Lower Limit	Upper Limit
Baseline			1
Week 12	84	2	126
Week 24	168	127	210
Week 36	252	211	294
Week 48	336	295	378
Week 60	420	379	462
Week 72	504	463	546
Week 84	588	547	630
Week 96	672	631	756
Week K (K is every 24 weeks after Week 96)	K*7	(K-12)*7+1	(K+12)*7

Table 3-4. Analysis Windows for HBV Serology for the All B/F/TAF Analysis

		B/F/TAF Group)	DTG	+ F/TDF to B/F	/TAF
Visit ID	Nominal Day	Lower Limit	Upper Limit	Nominal Day	Lower Limit	Upper Limit
Baseline			1			1
Week 12	84	2	126	NA	NA	NA
Week 24	168	127	210	NA	NA	NA
Week 36	252	211	294	NA	NA	NA
Week 48	336	295	378	336	2	504
Week 60	420	379	462	NA	NA	NA
Week 72	504	463	546	NA	NA	NA
Week 84	588	547	630	NA	NA	NA
Week 96	672	631	756	672	505	840
Week K	K*7	(K-12)*7+1	(K+12)*7	NA	NA	NA

NA = Not applicable

Note: For the B/F/TAF group, Study Day 1 is the first dose date of the B/F/TAF received in the randomized phase.

Note: For the DTG + F/TDF to B/F/TAF group, Study Day 1 is the first dose date of the B/F/TAF received in the extension phase

Note: Week K is every 24 weeks after previous visit in blinded phase and every 48 weeks in OL extension phase.

The analysis windows for metabolic assessments (including fasting glucose and lipid panel: total cholesterol, high density lipoprotein [HDL], direct low density lipoprotein [LDL], triglycerides, and total cholesterol to HDL ratio) are presented in Table 3-5 and Table 3-6.

Table 3-5 Analysis Windows for Metabolic Assessments for the Randomized Phase Analysis

Visit ID	Nominal Day	Lower Limit	Upper Limit
Baseline			1
Week 24	168	2	252
Week 48	336	253	420
Week 72	504	421	588
Week 96	672	589	756
Week K (K is every 24 weeks after previous visit)	K*7	(K-12)*7+1	(K+12)*7

Table 3-6 Analysis Windows for Metabolic Assessments for All B/F/TAF Analysis

	B/F/TAF Group			DTG	+ F/TDF to B/F	/TAF
Visit ID	Nominal Day	Lower Limit	Upper Limit	Nominal Day	Lower Limit	Upper Limit
Baseline			1			1
Week 24	168	2	252	168	2	252
Week 48	336	253	420	336	253	420
Week 72	504	421	588	504	421	588
Week 96	672	589	756	672	589	756
Week k	K*7	(K-12)*7+1	(K+12)*7	K*7	(K-12)*7+1	(K+12)*7

NA = Not applicable

Note: For the B/F/TAF group, Study Day 1 is the first dose date of the B/F/TAF received in the randomized phase.

Note: For the DTG + F/TDF to B/F/TAF group, Study Day 1 is the first dose date of the B/F/TAF received in the extension

Note: Week k is every 24 weeks after previous visit.

The analysis windows for renal function (including urine RBP and urine beta-1-microglobulin) are presented in Table 3-7.

Table 3-7 Analysis Windows for Renal Function for the Randomized Phase Analysis

Visit ID	Nominal Day	Lower Limit	Upper Limit
Baseline			1
Week 24	168	2	252
Week 48	336	253	504
Week 96	672	505	756

The analysis windows for HCV serology is presented in Table 3-8 and Table 3-9.

Table 3-8 Analysis Windows for HCV Serology and HCV RNA for the Randomized Phase Analysis

Visit ID	Nominal Day	Lower Limit	Upper Limit
Baseline			1
Week 48	336	2	504
Week 96	672	505	840
Week K (K is every 48 weeks after previous visit)	K*7	(K-24)*7+1	(K+24)*7

Table 3-9 Analysis Windows for HCV Serology and HCV RNA Assessments for the All B/F/TAF Analysis

	B/F/TAF Group			DTG + F/TDF to B/F/TAF		
Visit ID	Nominal Day	Lower Limit	Upper Limit	Nominal Day	Lower Limit	Upper Limit
Baseline			1			1
Week 48	336	2	504	336	2	504
Week 96	672	505	840	672	505	840
Week k	K*7	(K-24)*7+1	(K+24)*7	K*7	(K-24)*7+1	(K+24)*7

NA = Not applicable

Note: For the B/F/TAF group, Study Day 1 is the first dose date of the B/F/TAF received in the randomized phase.

Note: For the DTG + F/TDF to B/F/TAF group, Study Day 1 is the first dose date of the B/F/TAF received in the extension

nhase

Note: Week k is every 48 weeks after previous visit.

3.8.3. Selection of Data in the Event of Multiple Records in an Analysis Window

Depending on the statistical analysis method, single values are required for each analysis window. For example, change from baseline by visit usually requires a single value, whereas a time to event analysis would not require one value per analysis window. When a single value is needed, the following rule(s) will be used.

If multiple nonmissing numeric observations exist in a window, then records will be chosen as follows:

• For baseline, the latest available record on or prior to the first dose date of study drug will be selected. If there are multiple records with the same time or no time recorded on the same day, an average will be used for the baseline value, except for HIV-1 RNA (see below).

• For postbaseline visits:

- For CD4+ cell count and CD4%, the record(s) collected on the latest day in the window will be selected for analysis.
- For ALT, the record with the largest value in the window will be selected.
- For HBV DNA, the record closest to the nominal day for that visit will be selected. If there are 2 records equidistant from the nominal day, the latest will be selected. If there is more than 1 record on the selected day, the geometric mean will be taken.
- For other numeric observations (ie, except HIV-1 RNA, ALT, HBV DNA, CD4+ cell count, and CD4%), the record(s) collected on the day closest to the nominal day for that visit will be selected. If there are 2 days equidistant from the nominal day, the later day will be selected.
- For any numeric observations except HIV-1 RNA, ALT, and HBV DNA, if there are multiple records on the selected day, the average will be taken.

For baseline and postbaseline HIV-1 RNA, the latest (considering both date and time) record(s) in the window will be selected. If both "HIV RNA" (or "HIV-1 RNA Expedited" from China) and "HIV RNA Repeat" (ie, the HIV-1 RNA result obtained from an additional aliquot of the original sample) are available with the same collection time, the results from the "HIV RNA Repeat" will be selected for analysis purposes; otherwise, if there are multiple "HIV RNA" (or "HIV-1 RNA Expedited" from China) records with the same collection time, the geometric mean will be taken for analysis purposes.

If multiple valid nonmissing categorical observations exist in a window, records will be chosen as follows:

- For baseline, the last available record on or prior to the first dose date of study drug will be selected. If there are multiple records with the same time or no time recorded on the same day, the value with the lowest severity will be selected (eg, normal will be selected over abnormal for safety ECG findings).
- For postbaseline visits, the most conservative value within the window will be selected.
- For HBeAg, HBeAb, HBsAg, and HBsAb, the record closest to the nominal day for that visit will be selected. If there are 2 records equidistant from the nominal day, the latest will be selected. If there is more than 1 record on the selected day, the most conservative value will be taken, ie, positive will be selected over negative for HBeAg and HBsAg, and negative will be selected over positive for HBeAb and HBsAb.

In an analysis window (including baseline window), if both central lab and local lab results are available, then central lab results will be used for record selection instead of local lab results; local lab results will only be used for record selection if central lab results are missing.

